5.2 How supplied

buparlisib and Sonidegib will be dispensed at the start of every cycle, as needed.

5.2.1 Buparlisib

Novartis supplies buparlisib as 10-mg and 50-mg hard gelatin capsules. buparlisib will be administered orally once a day, as part of each 28-day cycle. Medication labels comply with the legal requirements of each country and will be printed in the local language. The storage conditions for study drug will be described on the medication label.

5.2.2 Sonidegib

Sonidegib will be supplied to the study investigators by Novartis. Sonidegib is formulated in capsules and tablets of 200-mg, strengths. The capsules are packaged in HDPE bottles with a child resistant closure. Sonidegib will be administered orally once a day, as part of each 28-day cycle.

Medication labels will conform to local legal requirements. Patient number will be added by the site pharmacist. The storage conditions for study drug will be described on the medication label. Sonidegib will be dispensed at the start of every cycle, as needed. Sonidegib will be administered orally once a day, as part of each 28-day cycle. The investigational site staff will inform each patient of their actual daily dose, and this will be recorded on the appropriate CRF.

When possible, individual doses will consist of the minimum number of capsules equaling the total dose given the available capsule sizes.

Doses for more than 7 days will be placed at 4₀ and patients will be informed of this at drug dispensing.

5.3 Storage and Preparation

The study drugs must be received at the study site by a designated person, handled and stored safely and properly, and kept in a secured location to which only the pharmacist and designated assistants have access. Upon receipt, the investigational drugs should be stored according to the instructions specified on the drug labels. Clinical supplies are to be dispensed only in accordance with the protocol.

The investigator must maintain an accurate record of the shipment and dispensing of study drug in a drug accountability ledger. Drug accountability will be noted by the field monitor during site visits and/or at the completion of the study. All drug supplies are to be used only for this protocol and not for any other purpose. Unless specifically instructed by Novartis, the investigator must not destroy any drug labels, or any partly used or unused drug supply. Only after receiving written authorization by Novartis, the investigator will be instructed to either send all of the unused and partly used drug supplies as well as the empty containers to the address provided at the time of authorization for destruction or to dispose of unused drug according to local regulations.

5.4 Disposal and destruction

The drug supply will be destroyed at a Novartis facility, Drug Supply group or third party, as appropriate. Study drug destruction at the investigational site will only be permitted if authorized by Novartis in a prior agreement and if permitted by local regulations.

6 **Data management**

6.1 Data collection

Investigators must record the information required by the protocol. The following analysis sets will be used for statistical analysis and data reporting.

The Full Analysis Set (FAS) consists of all patients who receive at least one (full or partial) dose of buparlisib and/or Sonidegib. Patients will be classified according to the assigned treatment.

Patients who are screened but never start treatment will be listed and will not be included in any of the summary tables.

The Safety Set consists of all patients who receive at least one (full or partial) dose of buparlisib and/or Sonidegib and have at least one valid post-baseline safety assessment. The statement that a patient has no adverse events (on the Adverse Event CRF) constitutes a valid safety assessment.

Patients will be classified according to treatment received, where treatment received for each drug is defined as (i) the treatment assigned if it was received at least once, or (ii) the first treatment received when starting study medication if assigned treatment is never received. Each patient will be classified into and analyzed consistently within one (and only one) treatment group.

The Dose-determining Set consists of all patients from the safety set who either meet the minimum exposure criterion and have sufficient safety evaluations (as determined by the investigators and Novartis), or have experienced a DLT during the first two cycles. This constitutes an evaluable patient for the determination of MTD.

A patient is considered to have met the minimum exposure criterion at a treatment group if a patient has been treated with at least 75% (ie, 42 days) of the planned 8 weeks (56 days) doses of buparlisib and Sonidegib and the patient has been observed for at least 8 weeks following the first dose, and has completed sufficient safety evaluations, as agreed by the investigators and the Sponsor, to determine whether a DLT has occurred or not.

The Biomarker Analysis Set (BAS) consists of all patients who receive at least one (full or partial) dose of buparlisib and LDE255 and provided at least one evaluable biomarker data.

6.1.1 Variables

- overall response rate (ORR) of LB therapy for patients with locally advanced or metastatic BCC in Smoothened inhibitor naive patients (Cohort 1) and those whose disease is refractory or relapsed on Smoothened inhibitor monotherapy (Cohort 2).
- median duration of response, on or after LB therapy
- frequency and severity of adverse events, including serious adverse events of LB therapy
- semi-quantitative evaluation of immunostaining for biomarkers including Gli 1, 2, PTCH, Sufu, Smoothened, PI3K markers and gene expression profiles at baseline and following 12 weeks of treatment

6.2 Analysis of the primary and key secondary variable(s)

Primary variables

•• Overall Response Rate by RECIST criteria will be assessed for cohorts 1 and 2.

Secondary variables

- ◆◆ Median duration of response will be assessed for cohorts 1 and 2.
- ◆◆ Frequency of adverse events on LB therapy
- ◆◆ Changes in gene expression profiles of BCCs including Hedgehog pathway and PI3K pathways
- ◆◆ Correlation of particular gene expression profiles and response to LB therapy

7 Statistical methods

7.1 Statistical Methods

7.1.1 Statistical model, hypothesis, and method of analysis

This is an exploratory study to assess the Overall Response Rate (ORR) and median duration of response (DOR) for LB therapy after 12 weeks of treatment. Cohort 1 and 2 will not be compared directly but will be described separately, due to sample size limitations.

Effect on Progression Free Survival and Overall Survival is beyond the scope of this proposal due to sample size necessary for sufficient power would require multi-center studies.

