4.3.3 Safety assessments

Patients enrolled in this clinical trial will be evaluated clinically and with standard laboratory tests before and at regular intervals during their participation in this study (see Study Calendar). Safety evaluations will consist of tumor assessments performed every 4 weeks, routine hematology, comprehensive metabolic profiles, EKGs and urinalysis.

^{**}Screening radiological assessments should be performed within 4 weeks of the first dose. Radiological tumor assessment should be performed at baseline within 28 days before start of treatment and subsequently every 8 weeks, until progression of disease or end of treatment. If stable after cycle 4, then CT scan to be performed every 12 weeks instead. All assessments should be performed within ± 7 days of the scheduled day of assessment. The assessment at the EOT visit is only to be performed if the prior assessment occurred ≥ 21 days before.

Tissue samples at baseline, week 12 and 24 (or EOT, whichever occurs first) will be taken and sent for whole exome sequencing, gene expression profiling and immunohistochemistry if accessible to tumor biopsy.

To date, Sonidegib has been shown to be well-tolerated in early phase clinical studies with the most common side effects consisting of fatigue, nausea, vomiting, anorexia, muscle cramps, and dysgeusia (5). To date, the most common adverse events of patients on buparlisib ($\geq 15\%$), regardless of grade and causality, reported in any treatment cycle were decreased appetite (45.5%), nausea (39.4%), constipation, diarrhea, fatigue (each 31.8%), rash (30.3%), hyperglycemia (27.3%), asthenia (25.8%), abdominal pain, vomiting (each 22.7%), anxiety (21.2%), depression (19.7%), mucosal inflammation, pruritus (each18.2%), dyspnea (16.7%), AST increase, dry skin, dyspepsia, pyrexia, and somnolence (each 15.2%), data provided by Novartis.

It is possible that the combination of the two medications, Sonidegib and buparlisib may lead to additive or synergistic side effects. Independently, both medications are known to cause frequent gastrointestinal side effects such as nausea and vomiting and the concomitant administration of both may compound these side effects.

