4.3.5.5 Neuropsychiatric assessments

Patient self-rating mood questionnaires for anxiety and depression (PHQ-9, GAD-7) will be applied at:

- **♦♦** Screening
- ◆◆ Days 1 and 15 of Cycle 1
- ◆◆ Day 1 and 15 of Cycle 2
- •• Day 1 of Cycle 3 and subsequent cycles (only for patients who have not shown mood alterations during the first 2 cycles, patients who did should continue to fill out the questionnaire on a weekly base).
- **♦♦** End of Study treatment

Additional assessments may be done according to the clinical judgment of the Investigator. Symptomatic patients (\geq CTCAE Grade 1) must continue with questionnaires on a weekly basis while active on the treatment portion of the study. Instructions on how to instruct the patient to complete the questionnaires as well as how to determine the scores will be provided together with each instrument. This will be done as an online HIPPA compliant survey tool through Stanford.

4.3.5.6 **ECG/ECHO**

A standard 12 lead ECG is to be performed at screening and as clinically indicated. An echocardiogram (ECHO) or MUGA will be performed to assess eligibility. ECHO/MUGA will be repeated at Cycle 4 and then every 4th cycle thereafter.

4.3.5.7 **Performance status**

Performance status will be assessed at screening and per the visit schedule. ECOG will be used for assessment (See Appendix A).

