4.3.5.8 Special tests

Chest X-ray

Will be performed at baseline and every 8 weeks for monitoring per standard protocol.

CT scan

Will be performed at baseline, at 4 weeks and every 8 weeks thereafter for tumor assessment of non-visible tumors per RECIST 1.1 protocol. If CT scans show stability after cycle 4, then CT scan to be performed every 12 weeks instead.

Biomarkers

- ◆◆ Tissue samples at baseline, week 12 and 24 (or EOT, whichever occurs first) will be taken and sent for whole exome sequencing, gene expression profiling and immunohistochemistry. Whole exome sequence will include interrogation for DNA mutations in the tumor and peripheral blood. Gene expression analysis will identify increases or decreases in pathways including Hedgehog and PI3K. Immunohistochemistry to quantify protein levels of Gli 1,2, Ptch 1,2, PI3K in semi-quantitative fashion will be performed to confirm expression analysis results.
- ♦♦ Whole exome sequencing and gene expression analysis may identify novel resistance mechanisms in these BCCs that would be useful to inform future clinical trials

5 Investigational agent sampling and shipping information

[name], or her designated associate will receive study medications at the Stanford Investigational Pharmacy, Redwood City, CA.

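### Imaging calendars for non-visible tumors conflict, the 12-week ORR has no response rule, and the DOR censoring date does not match how visible tumors are read

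*Combined protocol and SAP*

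**What the plan says.** **Endpoint timing.** Section 7.1.1 describes an exploratory assessment of "Overall Response Rate (ORR) and median duration of response (DOR) for LB therapy after 12 weeks of treatment". The objectives (Section 2), the variables (Section 6.1.1) and the analysis list (Section 6.2) name ORR and median DOR with no time point. Treatment continues until progression, intolerable toxicity or withdrawal (Section 3.1).

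**How tumors are read.** Under Section 4.3.2, a target tumor visible on the skin is measured by caliper and one that is not visible is imaged. RECIST 1.1 applies.

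**When tumors are read.**
- Table 19 footnote: imaging at baseline and "subsequently every 8 weeks, until progression of disease or end of treatment", with "All assessments should be performed within ± 7 days of the scheduled day of assessment".
- Section 4.3.5.8, CT scan, for non-visible tumors: "Will be performed at baseline, at 4 weeks and every 8 weeks thereafter".
- Section 4.3.5.4: a tumor exam at each visit, by diameter if the tumor is visible and by imaging if it is not.
- Section 4.3.3: "Safety evaluations will consist of tumor assessments performed every 4 weeks", with no method stated.

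**Censoring.** For patients still on drug at data cut-off, Section 7.1.2 censors time-to-event data, DOR included, at the most recent radiological evaluation before the cut-off. It does not mention the caliper reading.

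**The concern.** ORR is the primary objective, and each cohort has 12 patients. A reader cannot tell from the plan when a non-visible tumor is scanned, or whether a response first seen after week 12 counts. If week 12 is a fixed reading time, patients read by imaging and patients read by caliper in the same cohort could be judged at different times. If it is not, the calendar still fixes when a response is first recorded, and so when DOR starts.

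The censoring rule raises a second problem. DOR follow-up should end at the last assessment able to show that the response still holds. For a visible tumor that is a caliper reading, but the rule names a radiological date.

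**Working it through.** The plan states no alpha, power or target rate, so there is no figure of its own to reproduce. The check lays the stated calendars side by side.

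**Step 1. Calendars in weeks.** Cycles are 28 days (Section 5.2), so Day 1 of cycle c is week 4 × (c − 1). Week 12 is Day 1 of Cycle 4, which is also the end of Cycle 3.

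| Source | Weeks | Assessment within 7 days of week 12? |
|---|---|---|
| Table 19 footnote | 8, 16, 24 | No |
| Section 4.3.5.8, CT | 4, 12, 20 | Yes |
| Section 4.3.5.4, read literally | every visit | Yes |
| Section 4.3.3, no method stated | 4, 8, 12, 16 | Yes |

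Under the footnote, the week-8 scan can be as late as 8 + 1 = week 9 and the week-16 scan as early as 16 − 1 = week 15. Each is 3 weeks from week 12.

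**Step 2. The Table 19 grid does not settle it.** Radiology is marked at Cycles 3, 5 and 7. That is weeks 8, 16 and 24 if columns mean Day 1, or weeks 12, 20 and 28 if they mean end of cycle. The biopsy row is marked at Cycles 3 and 6 and footnoted "Tissue samples at baseline, week 12 and 24 (or EOT, whichever occurs first"), which fits end of cycle. Section 4.3.5.5 schedules the questionnaires on "Day 1 of Cycle 3 and subsequent cycles", which fits Day 1. The table may also be damaged in extraction, so nothing below relies on it.

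**Step 3. If ORR means response at week 12.** Take a non-visible tumor that first responds between weeks 8 and 12. Under Section 4.3.5.8 it is seen at week 12 and counts. Under the footnote it is seen at week 16 and does not. A visible tumor with the same course has a caliper reading at the week-12 visit and counts. One reclassified patient is worth 1/12 = 8.3 points. For illustration, with exact (Clopper-Pearson) 95% intervals:
- 4/12 = 33.3% (9.9 to 65.1)
- 5/12 = 41.7% (15.2 to 72.3)

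**Step 4. If ORR means best response.** The responder count is mostly the same, but the week a response is first seen differs (scans on schedule, before any switch to 12-weekly CT):

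| Onset week | Footnote | Section 4.3.5.8 | Difference |
|---|---|---|---|
| 2 | 8 | 4 | +4 |
| 6 | 8 | 12 | −4 |
| 10 | 16 | 12 | +4 |
| 14 | 16 | 20 | −4 |

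With the progression date held fixed, an individual DOR moves by the same 4 weeks in the opposite direction.

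**Step 5. Censoring date for visible tumors.** Metastatic patients must have a target lesion measurable by CT or MRI (Section 3.2.2.1). The issue is therefore locally advanced disease with a visible tumor. The radiological term in Section 7.1.2 has two literal readings:
- The CT/MRI row of Table 19, which applies when the tumor is not clinically visible. These patients may then have no radiological tumor assessment after baseline. Any baseline scan precedes the response, so it gives no usable DOR.
- The chest X-ray, a separate row for locally advanced disease ("Will be performed at baseline and every 8 weeks for monitoring per standard protocol"). A date then exists, but it is not the date of the reading that defines response.

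**The case against.** The strongest reply is that the 12-week phrase is loose. It covers ORR and DOR together, and a DOR fixed at 12 weeks makes little sense when treatment runs to progression. Best response fits Sections 2, 6.1.1 and 6.2 better, and under it ORR barely moves. This stands. A reader might infer that the plan fixes ORR at week 12, or that DOR will be cut off there; the documents support neither. But no section writes a best-response rule either, so the definition is still missing.

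The literal wording of Section 4.3.5.4 would put imaging at about week 12 for non-visible tumors. This stands as a further schedule, so it cannot be said flatly that imaging and caliper patients are read at different times. It adds to the conflict and does not resolve it.

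The 4-weekly line in Section 4.3.3 concerns safety evaluations and is compatible with a tumor exam at each visit. Agreed: it need not contradict either imaging calendar. The conflict rests on the Table 19 footnote and Sections 4.3.5.4 and 4.3.5.8.

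On censoring, the radiological term may simply be meant as the response assessment, by whatever method. Also, the footnote does not limit 8-weekly imaging to non-visible tumors. Either could be the intention, and then the repair is purely one of wording. The text does not say so.

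Finally, the study is descriptive, with no test, no threshold and no comparison of cohorts. An 8.3-point shift is small beside intervals 55 to 57 points wide (65.1 − 9.9 = 55.2; 72.3 − 15.2 = 57.1). That limits the consequence. Still, the estimates are the study's product, and Section 1.1 presents them as critical for later, larger studies.

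**Conclusion.** The point holds as an inconsistency in the plan. The imaging rules for non-visible tumors are incompatible, the response rule behind ORR is unstated, and the DOR censoring rule does not match how visible tumors are measured. All three follow from plain text.

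The size depends on what is meant. Under week-12 response it is 8.3 points of ORR per reclassified patient in a cohort of 12. The number of such patients cannot be estimated, because the documents do not say how many tumors are read only by imaging or when responses begin. Under best response, ORR is mostly unchanged and first-seen dates move 4 weeks in either direction. In the four onset weeks shown these shifts sum to zero, so they show uncertainty in dating and not a bias of known sign. The effect on median DOR was not calculated.

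For censoring, a reader might infer a fixed loss of follow-up or a complete absence of dates. Neither is established, since that depends on whether a chest X-ray counts as a radiological disease assessment. What can be said is that the named date may be missing, or may not be the date of the reading that defines response.

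**What to change.** 1. Reconcile the Table 19 footnote, Section 4.3.5.4 and Section 4.3.5.8 to one imaging calendar for non-visible tumors, and state whether the Table 19 cycle columns mean Day 1 or end of cycle.
2. In Section 7.1.1, state whether ORR is best response by RECIST 1.1 or response at week 12. If week 12, schedule the imaging and caliper readings at that same time, with a window. Section 4.3.5.8 already contains a week-12 scan.
3. Remove the 12-week qualifier from DOR.
4. In Section 7.1.2, censor DOR at the last adequate tumor assessment before the cut-off, caliper or imaging, by the method that defines that patient's response.

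These are wording changes with no effect on sample size. The downside is that some scan dates shift at the single center, depending on which calendar is now followed.

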7.1.2 Handling of missing values/censoring/discontinuations

Patients will not be replaced in this protocol. However, additional patients may be enrolled to ensure an adequate number of evaluable patients.

As of the date of data-cutoff for the purposes of reporting:

- ◆◆Patients continuing to receive study drug will have time-to-event data (eg, progression free survival, duration of response, etc.) censored at the date of last radiological disease assessment prior to the cut-off date.
- ◆◆Continuing events (eg, adverse events, concomitant medication, etc.) will be summarized using the data cut-off date as the date of completion, with an indication within listings that the event is continuing.

For patients who discontinue the study with ongoing events, the discontinuation date will be used as the completion date of the event with the appropriate censoring as described in the above paragraph.

The reason for discontinuation from study will be summarized and listed, along with dates of first and last study drug, duration of exposure to study drug and date of discontinuation for each patient, by dose cohort in the core safety report and by dose-expansion part in the extension report

8 References

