4.3 Visit schedule and assessments 4.3.1 Evaluation and Visit Schedule (Table 19)

Examination	Screening	Cycle 1		Cycle 2		Cycle 3 to Cycle n					
Day of Cycle	-21	1 (Baseline)	15	1	15	3	4	5	6	7	
Informed consent	X										
Medical History	Х										
Inclusion/ exclusion criteria	X										
Serum pregnancy test (with 72 hours of 1 st treatment for WOCBP)	As clinically indicated.										
Urinalysis	Х										
Vital signs	Х	Х	Х	Х	Х	Х	Х	Х	Х	Х	Х
Physical examination (including skin rash assessment)	Х	X		Х		X	Х	X	Х	X	Х
Performance Status ECOG	Х	Х		Х		Х	Х	Х	Х	Х	Х
Neuro-psychiatric assessment (self-rating mood questionnaire GAD and PHQ)	х	Х	X	X	X	Х	Х	X	Х	Х	Х
Examination	Screening	Cycle 1		Cycle 2		Cycle 3 to Cycle n					
Day of Cycle	-21	1 (Baseline)	15	1	15	3	4	5	6	7	
12-lead ECG*	Х	As clinically indicated.									
Chest X-Ray (if locally advanced disease only)	Х	Every 8 weeks from start of treatment until progression as per RECI									

Radiological tumor	Х					Х		Х		Х	
assessment/response											
assessment (CT or MERI											
Scans if no clinically											
visible)**											
Hematology*	Х	X	X	X	Х	Х	Х	Х	Х	Х	
Serum Chemistry*	Х	Х	Х	Х	Х	Х	Х	Х	Х	Х	
Coagulation Profile*	Х			Х			Х		Х		
Fasting plasma glucose*	Х	Х	Х	Х	Х	Х	Х	Х	Х	Х	
HgA1C*	X					X			X		
Tumor biopsy for biomarkers ³	Х					Х			Х		

^{*} Can use screening if w/in 72 hours of baseline.

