4.3.2 Efficacy assessments

Efficacy will be assessed on the basis of clinical examination using calipers if the target tumor is visible on the skin. If it is not visible on the skin tumor imaging will be used to assess the single longest diameter for the basis of efficacy assessment. (see 4.3.1 Evaluation and Visit Schedule (Table 19). Tumor response by RECIST 1.1 criteria will be used for evaluation.

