4.3.5.4 Physical examination

Physical examination will be performed which must comprise a total body examination (general appearance, skin, neck, including thyroid, eyes, ears, nose, throat, lungs, heart, abdomen, back, lymph nodes, extremities and basic nervous system). Significant findings made after the start of study drug which meet the definition of an Adverse Event must be recorded. Tumor exam will be done at each visit and will include measurements of single largest diameter of visible tumor or radiographic imaging for tumors that are not clinically visible.

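### Section 7.1.2 censors duration of response at the last radiological assessment, a test that does not define response for patients whose tumours are measured by calipers

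*Combined protocol and SAP*

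**What the plan says.** Section 7.1.2 covers patients still receiving drug at data cut-off. Their time-to-event data, with DOR named as an example, are "censored at the date of last radiological disease assessment prior to the cut-off date". The same section continues: "For patients who discontinue the study with ongoing events, the discontinuation date will be used as the completion date of the event", and then refers back to the censoring just described.

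The method of tumour assessment is set elsewhere:

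- Section 4.3.2: "Efficacy will be assessed on the basis of clinical examination using calipers if the target tumor is visible on the skin". Imaging is used when the tumour is not visible.
- Section 4.3.5.4: "Tumor exam will be done at each visit and will include measurements of single largest diameter of visible tumor", with imaging for tumours that cannot be seen clinically.
- Section 4.3.5.8: CT at baseline, at 4 weeks and "every 8 weeks thereafter for tumor assessment of non-visible tumors per RECIST 1.1 protocol", moving to every 12 weeks if stable after cycle 4.
- Table 19 (section 4.3.1): one row combines radiological tumour assessment and response assessment. Its label, broken in the available copy, limits CT or MRI with the words "Scans if no clinically" visible.
- Table 19, chest X-ray row, for locally advanced disease only: "Every 8 weeks from start of treatment until progression as per RECI". Section 4.3.5.8 describes this film as monitoring.
- Table 19 footnote, which falls within the text of section 4.3.3: "Radiological tumor assessment should be performed at baseline within 28 days before start of treatment and subsequently every 8 weeks". It does not repeat the limit to non-visible tumours.

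Median DOR by cohort is a secondary variable (section 6.2). The objective in section 2 counts response both during and following the combination.

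**The concern.** A censoring date should come from the assessment that last showed the patient to be still in response. For a tumour followed by calipers, that is the last caliper measurement. Section 7.1.2 uses a radiological date instead, and nowhere do the documents give a censoring date based on calipers.

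If radiological means CT or MRI, a patient with only visible disease may have no scan after screening. While in response that patient gets a censoring date before response started, or none. A similar patient who progresses still counts as an event. Follow-up is lost only from those doing well, so the estimated median DOR is too short.

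The paragraph on discontinuation adds a second uncertainty. For a responder who leaves without progression it points both to the discontinuation date and to the radiological rule. It does not address a patient who stops drug but is still being assessed.

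**Working it through.** The plan states no figure for this point, so there is none to reproduce. The check has three parts.

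**1. What date does each reading give?** Censored DOR = week of censoring − week of first response. Assume an ongoing responder with visible disease only, response first seen at week 8, cut-off at week 48, 4-weekly caliper visits and 8-weekly films.

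| Reading of the rule | Censoring week | Censored DOR (weeks) |
|---|---|---|
| A. CT/MRI only | −4 to 0 (screening scan), or none | −12 to −8, or undefined |
| B. Chest X-ray counts | 40 | 40 − 8 = +32 |
| Caliper visit (the proposed fix) | 44 | 44 − 8 = +36 |

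Two further readings also give a usable date. C: the combined Table 19 row is one scheduled response assessment for everyone, by calipers where the tumour is visible. D: the Table 19 footnote means imaging for everyone, 8-weekly and later 12-weekly if stable.

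**2. Direction of the effect.** The documents name no estimator; Kaplan-Meier is assumed, with S(t) = ∏(1 − d/n) and the median at the first time S ≤ 0.5. Take 6 responders: 2 progress at 16 and 24 weeks, and 4 are still responding at 40 weeks. Let k of those 4 be visible-only and lose their follow-up under A.

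- k = 0: S(24) = 5/6 × 4/5 = 0.667; median not reached.
- k = 1: S(24) = 4/5 × 3/4 = 0.60; not reached.
- k = 2: S(24) = 3/4 × 2/3 = 0.50; median 24 weeks.
- k = 3: S(16) = 0.667 and S(24) = 2/3 × 1/2 = 0.333; median 24 weeks.
- k = 4: S(16) = 1/2 = 0.50; median 16 weeks.

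With caliper or X-ray dates after week 24, the median is not reached for any k.

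**3. How often the median would change.** All inputs here are assumptions.

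- Responders: 4, 5 or 6 per cohort. The only anchor is the 38% response among BCC patients in section 1.4.7.2.2; 0.38 × 12 = 4.6.
- DOR: exponential, true median 26, 52 or 104 weeks.
- Follow-up after response: uniform, 26 to 104 weeks.
- Each responder visible with probability 0.5.
- Under A, an ongoing visible responder is censored at 0. Under B, censoring is up to 8 weeks early, uniformly.

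Share of simulated trials in which the estimated median differs from the one using caliper dates:

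| Responders | A, true median 26 / 52 / 104 weeks | B |
|---|---|---|
| 4 | 6% / 18% / 26% | under 4% |
| 5 | 40% / 56% / 47% | under 4% |
| 6 | 12% / 34% / 40% | under 4% |

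The rate is higher at 5 because of the median convention. Uncensored, 5 responders need 3 events to reach S ≤ 0.5; losing one leaves 4, who need only 2. With 6 or 4 responders, losing one leaves the number needed unchanged, at 3 or 2.

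Typical estimated medians with half visible are 20 / 43 / not reached (caliper dates) against 19 / 33 / 56 weeks (A) for 6 responders, and 26 / 55 / not reached against 20 / 32 / 54 weeks for 5. Under A the share of trials affected depends heavily on the visible share: with 6 responders it is 4-15% at 25% visible and 37-87% at 100%.

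**The case against.** The strongest reply is that nobody would apply reading A. It gives negative durations for the patients at the centre of a skin-cancer trial, and an analyst would probably notice. The phrase in section 7.1.2 also resembles the combined Table 19 row, which has a single schedule and appears to treat CT or MRI as the method when the tumour is not visible. On that view the date is simply the last scheduled response assessment. The footnote carries no visible-tumour exception, and locally advanced patients have an 8-weekly film in any case.

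Much of this stands. It is why the point is an ambiguity with one harmful reading. A reader might infer that the plan will discard ongoing visible-tumour responders, or that reported medians will be too short. The documents do not support that, because three of the four readings give a usable date. They do not settle the matter either. The row is broken in the available copy, the footnote belongs to a row that carries the limit, section 4.3.5.8 restricts CT to non-visible tumours, and the chest film is not described as measuring the target. If the problem is noticed only at analysis, the rule would be chosen after seeing the data.

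The illustration is also open to criticism. The 38% comes from 6 of 16 patients on sonidegib alone in a dose-escalation study, and is no basis for Cohort 2, whose disease is refractory or relapsed on Smoothened inhibitors. The visible share and follow-up are not in the documents, and section 7.1.1 speaks of assessment after 12 weeks of treatment. Treating every ongoing visible responder as censored at 0 assumes that all are still on drug, the only group the rule plainly covers. The percentages show what could happen under A and are not a forecast.

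**Conclusion.** The mismatch is real and the point holds as a minor one. Section 7.1.2 ties DOR censoring to a test that does not define response in visible-tumour patients. These are mainly locally advanced patients, because metastatic patients need a target measurable on CT or MRI (section 3.2.2.1).

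On the literal CT/MRI reading, the censoring date is before response or missing, and a Kaplan-Meier median is biased downward. On the other three readings the effect is small; only the chest X-ray reading was quantified above. The actual size cannot be known, since it depends on the reading adopted, the number of responders, the visible share and the follow-up.

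It would be wrong to extend this to the primary endpoint. The overall response rate uses no censoring date and is unaffected. DOR is a secondary, descriptive endpoint in a pilot with 12 patients per cohort.

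**What to change.** In section 7.1.2:

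1. Replace the radiological date for DOR with: *last evaluable tumour assessment (caliper or imaging) by the method used to define response for that patient*.
2. Add that a chest X-ray alone does not set the date for a caliper-measured target.
3. In the discontinuation paragraph, add that a patient who leaves the study while in response is censored for DOR at the last evaluable tumour assessment on or before study discontinuation. Say that stopping study drug alone does not censor DOR if tumour assessments continue, because the endpoint includes response after therapy. Confine the discontinuation-date rule to continuing events such as adverse events and concomitant medication.

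The cost is wording in two adjacent paragraphs. Caliper measurements are already taken at each visit, so no new data or visits are needed. The change should be made before data cut-off.
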